Official Title of the study:

Helmet CPAP versus High Flow Nasal Cannula Oxygen in Acute
Cardiogenic Pulmonary Oedema: A Randomized Control Trial

Date of Document:

31st May 2018

Objective:

To our knowledge, there has been no randomized trial comparing hCPAP with HFNC for management of patients with ACPE. The aim of this study was to compare the effectiveness of hCPAP with HFNC in emergency department in the management of ACPE, in terms of physiological outcomes, patient's comfort, intubation rate, and 28-days mortality.

Design:

This is a single center, randomized, controlled trial. The study was conducted from January 2018 to December 2018 in Emergency Department, Raja Permaisuri Bainun Hospital, Perak, Malaysia

Methods:

A randomization sequence was generated using Microsoft Excel Version 14.3.9 (Microsoft Corporation Redmond, WA) using permuted block randomization technique. Sequentially numbered, sealed and opaque envelopes were used to conceal randomized allocation. The person responsible for the randomization was not part of the clinical team. Participants were assigned to receive either helmet CPAP or HFNC in a 1:1 ratio.

Ethical approval from Medical Research and Ethics Committee of Malaysia Ministry of Health had been granted [NMRR-17-1839-36966 (IIR)]. Written informed consent was obtained from patient whenever possible or from the next of kin. An external data monitoring committee supervised data collection.

Participants

All patients diagnosed with ACPE was defined by sudden onset of dyspnea; presence of bilateral rales on auscultation, compatible physical examination (elevated jugular venous pressure, third heart sound on cardiac auscultation) with no medical history suggesting pulmonary aspiration or infection; or congestion found on chest radiograph [1].

Patients meeting all the following inclusion criteria (1) age \geq 18 years (2) respiratory rate $>$ 30 breath per minute and (3) pulse oximetry saturation (SpO_2)

< 90% with oxygen > 5 L per minute via reservoir facemask were included. Patient were excluded if they have one or more of the following criteria (1) altered mental status (GCS \leq 14) (2) need for urgent intubation (3) hemodynamically unstable, or (4) pulmonary edema was believed to be non-cardiogenic causal.

Protocol

Upon arrival patients were supported on high flow non-rebreathing facemask with reservoir of oxygen 15 L/min. After enrolment they were randomized to receive either hCPAP or HFNC.

The helmet (CASTAR, Starmed, Italy) has gas inlet and outlet ports. The inlet port was connected to air and oxygen blender (Air Liquide, France). The outlet port was connected to a mechanical spring PEEP valve. Patient neck circumference was measured to ensure a tight but comfortable seal. The gas flow was set at minimum 40 L/min. PEEP was initially set at 5 cmH₂O with increments of 3-5 cmH₂O to achieve oxygen saturation of 94 -97%. Inspired oxygen fraction (FiO₂) was set at 0.6 and maintained throughout the treatment.

HFNC (Hamilton, C3S, INTELLiVENT, Switzerland) consists of an air-oxygen blender, which permits accurate adjustment of FiO₂ between 0.21 and 1.0 and delivery of gas flow up to 60 L/min through a heated humidifier (Hamilton H900, Switzerland). The gas mixture flows through a circuit at temperature of 37 °C and an absolute humidity of 44 mg/L to the patients. Large or medium nasal cannula were chosen according to patients' nostril size to limit air contamination. HFNC was first set at a gas flow of 50 L/min and a FiO₂ of 1.0, then was titrated to maintain SpO₂ of 94 – 97%.

In addition to the study intervention, patients received standard treatment consists of intravenous infusion of isosorbide dinitrate at initial rate of 1mg/hr, increased up to 10 mg/hr. Intravenous furosemide bolus of 40 mg or equal to patient pre-existing oral dosage were given if systolic blood pressure > 100 mmHg [1]. No sedative agent was given to patients. After the end of 60-

minute protocol, the chosen modality was continued at the discretion of the treating physician.

Early termination criteria included failure to tolerate NIV, worsening of respiratory failure (respiratory > 35 breaths/min, SpO₂ < 92%, PF ratio < 200, or signs of increased work of breathing such as use of accessory muscle), pulse rate > 120 beat/min or 30% increased above baseline, mean arterial pressure (MAP) increased > 30% above baseline prior intervention and deterioration of conscious level. If one or more of the criteria were encountered, intervention was escalated to intubation and mechanical ventilation. These patients were excluded from the final data analyses. The decision was made by the managing physician without the involvement of the researcher team.

Respiratory rate, heart rate, systolic and diastolic blood pressure, peripheral capillary oxygen saturation, arterial blood gaseous were obtained before beginning of the ventilation procedure and at 1 hour of ventilation. At these points, HACOR score, dyspnea scale using Visual Analogue Scale (VAS) and Likert scale were also obtained.

Dyspnea score measured using an unmarked 10cm VAS card that had mark with “I can breathe normally”, at one end correspond to patients’ normal baseline breathing which score “0” and on the other end “I can’t breathe at all”, which score “10” represent the worst difficulty perceived by patients [2].

HACOR is an acronym for heart rate, acidosis (pH), consciousness (GCS), oxygenation (PF ratio) and respiratory rate in which each parameter is an independent predictor for NIV failure [9]. HACOR score is out of 25 with differential weighting of each parameter. A HACOR score > 5 at 1 hour of NIV predicts > 80% risk of NIV failure and that early intubation guided by this score significantly improved mortality [3].

Study End Points

The primary outcome was a reduction in respiratory rate from prior to randomization to at 1 hour of treatment. The respiratory rate was measured directly by investigators, who auscultated and counted the breaths sound for

one full minute with a stethoscope. Secondary outcomes were improvements in (1) heart rate; (2) HACOR score; (3) arterial oxygenation PaO₂; (4) PF ratio; (5) dyspnea score; (6) intubation rate and (7) mortality rate 28-days.

Sample Size

Sample size calculation was obtained using G*Power Software version 3.1.9.4 by Franz Faul, University of Kiel, Germany (Copyright 1992-2019). Based on previous work, after 1 hour of intervention, there is a reduction in respiratory rate from 31 breaths/min (SD 3.7) to 22 breaths/min (SD 4.1) in HFNC group compared with a reduction of only 31 breaths/min (SD 3.9) to 25 (SD 3.6) breaths/min in control group [4]. We calculated sample size of 94 patients per group is necessary to get a trial power of 90%, a 1% type I error (2-sided tests) and 10% attrition rate.

Statistical Analysis Plan:

Data analyses were performed using SPSS (Ver.22 2013 IBM Corporation, USA). Data were analysed on the basis of priori-modified intention to treat. For continuous variables, results for each group are presented as means (SD) or median (interquartile range), according to the data distribution shape and type (nominal or ordinal). Dichotomous data are presented as number and percentage.

Primary outcome of respiratory rate difference and other normally distributed secondary outcomes were calculated using repeated measure ANOVA, a generalized mixed model with a compound-symmetry covariance matrix. Ordinal or skewed numerical data were analysed using Mann-Whitney U Test. Chi-square tests (or two-tailed Fisher exact tests when appropriate) were performed for categorical data. All tests were two-tailed with p-value of less than 0.05 were considered statistically significant.

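### The PF < 200 early-termination limit is an absolute value that does not identify worsening, yet meeting it leads to intubation and removal from the analysis

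*Combined protocol and SAP*

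**What the plan says.** All of this is in the Protocol section of the combined protocol and SAP unless noted.

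- **Helmet arm.** "Inspired oxygen fraction (FiO₂) was set at 0.6 and maintained throughout the treatment". PEEP starts at 5 cmH2O and is raised in steps "to achieve oxygen saturation of 94 -97"%.
- **HFNC arm.** "HFNC was first set at a gas flow of 50 L/min and a FiO₂ of 1.0", "then was titrated to maintain SpO₂ of 94 – 97"%.
- **Early termination.** The criteria include "worsening of respiratory failure (respiratory > 35 breaths/min, SpO₂ < 92%, PF ratio < 200", or signs of increased work of breathing. The MAP criterion, and one of the two pulse limits, are set relative to baseline. The PF limit is not.
- **Consequence.** "If one or more of the criteria were encountered, intervention was escalated to intubation and mechanical ventilation". Then: "These patients were excluded from the final data analyses". The managing physician takes the decision, without the research team.
- **Timing.** Blood gases are scheduled before ventilation starts and at 1 hour. After 60 minutes the modality is left to the treating physician.
- **Entry (Participants).** SpO2 must be below 90% on more than 5 L/min by reservoir mask.
- **Outcomes (Study End Points).** The primary outcome is the fall in respiratory rate at 1 hour. PF ratio, intubation rate and 28-day mortality are among the secondary outcomes.
- **Analysis set (Statistical Analysis Plan).** A modified intention-to-treat basis is named, but the modification is not defined.

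**The concern.** A criterion filed under worsening should separate patients who are getting worse from those who are stable or improving. A fixed PF of 200 may not do so here. It may be met by patients who are exactly where the protocol wants them, and by most patients before treatment starts.

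Three results are at stake. If the rule is applied as written to the 1-hour gas:

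- patients on target are sent to intubation, which is itself an outcome, and then removed, so those intubations do not enter the reported rate;
- the PF-ratio outcome is cut off below 200;
- the primary comparison loses the same patients.

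If physicians do not apply the rule literally, then whether a PF below 200 ends a patient's participation becomes an unrecorded judgement by someone who can see which device is in use. The documents do not show which of these happened.

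**Working it through.** The plan gives no figure to reproduce here. It also gives no conversion from SpO2 to PaO2, so a standard dissociation curve is assumed.

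**Formulas.** PF = PaO2 / FiO2. Saturation S = 1 / (23400 / (P³ + 150P) + 1), where P is PaO2 in mmHg at pH 7.4. For other pH values, PaO2 is multiplied by k = 10^(0.48 × (7.4 − pH)).

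**1. Helmet patient on target, pH 7.4.** Inverting the curve gives PaO2 of 70.9 mmHg at 94% and 90.6 mmHg at 97%. At FiO2 0.6:

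- 70.9 / 0.6 = 118
- 90.6 / 0.6 = 151

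A PF of 200 needs PaO2 = 200 × 0.6 = 120 mmHg, which is a saturation of about 98.7%.

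**2. Effect of pH.**

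| pH | k | Helmet PF at 94–97% | SpO2 needed for PF 200 at FiO2 0.6 |
|---|---|---|---|
| 7.5 | 0.895 | 106–135 | 99.0% |
| 7.4 | 1.000 | 118–151 | 98.7% |
| 7.3 | 1.117 | 132–169 | 98.2% |
| 7.2 | 1.247 | 147–188 | 97.5% |

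The whole target band lies below PF 200 at each of these pH values. Hill curves with P50 of 26.8–30 mmHg give 120–181. On-target PF reaches 200 only at the extremes: at pH 7.1 the band is 165–210, and with an oximeter reading 2 points low it is 137–220.

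**3. HFNC patient on target.** The FiO2 at which PF equals 200 is PaO2 / 200. At pH 7.4 this is 70.9 / 200 = 0.35 at SpO2 94% and 90.6 / 200 = 0.45 at 97%. The range is 0.32–0.41 at pH 7.5 and 0.44–0.57 at pH 7.2. Above that FiO2, an on-target HFNC patient meets the limit. At the starting FiO2 of 1.0, on-target PF is 71–91.

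**4. Before treatment.** SpO2 below 90% means PaO2 below about 58.7 mmHg at pH 7.4. PF is then below 200 whenever the mask delivers an FiO2 above 58.7 / 200 = 0.29. At pH 7.2 the figures are 58.7 × 1.247 = 73.2 mmHg and 73.2 / 200 = 0.37. The documents do not give mask FiO2. If 0.6 is assumed, entry PF is below 58.7 / 0.6 = 98.

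**5. Direction of change.** Under that assumption, a helmet patient who goes from entry to the target moves from a PF below 98 to 118–151. This patient has improved by at least a fifth (118 / 98 = 1.20) and still meets a criterion listed as worsening.

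**The case against.** The case on the other side has real force, and several stronger readings that a reader might infer do not hold.

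**That the rule works against the helmet arm.** HFNC can lower FiO2 and the helmet arm cannot, so this is tempting. But PF already divides by FiO2, and lowering FiO2 lowers PaO2 too. If PF is taken as roughly constant for a given lung (an assumption), an HFNC patient with PF 130 turned down to FiO2 0.40 has PaO2 130 × 0.40 = 52 mmHg. That is SpO2 of about 86%, off target and still below 200. An HFNC patient who needs FiO2 0.6 to stay on target has the same PF of 118–151 as a helmet patient. Conversely, the plan has no step that lowers helmet support above 97%. A helmet patient with PF 250 has PaO2 250 × 0.6 = 150 mmHg, reads about 99.3% and passes. PF does vary somewhat with FiO2, so a residual difference is possible, but nothing in the documents shows or sizes it.

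**That the bracketed limits contradict each other.** They are alternative triggers joined by an or. One firing while another does not is how such a list works.

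**That the PF limit should be dropped or set far lower.** A patient at 94–97% on FiO2 0.6 with PEEP still has poor gas exchange. The plan itself names PF among the predictors of NIV failure. Loosening a safety threshold is a clinical decision that the documents do not support.

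**That on-target patients were in fact intubated.** The physician decides, and no scheduled on-treatment gas falls before 1 hour. The rule could act only on an unscheduled gas or on the 1-hour gas, and the text does not say whether it applies to the latter.

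These points limit how often the rule acts and what can be said about the arms. They do not change the fact that the limit is absolute, that typical on-target patients can meet it, or that terminated patients are removed from the analysis.

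**Conclusion.** The point stands in a limited form. As written, PF < 200 is an absolute trigger for intubation and exclusion. A helmet patient on target meets it at PF of about 118–151 (106–188 over pH 7.5 to 7.2). An HFNC patient on target meets it at any FiO2 above about 0.35–0.45 at pH 7.4. Nearly all patients are below 200 before treatment, provided the mask delivers more than about 0.29 (0.37 at pH 7.2). The limit therefore marks persisting hypoxaemia and not deterioration.

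These figures rest on the assumed curve and on the oximeter being accurate to within about a point. The number of patients affected and any difference between arms cannot be computed.

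The exclusion of terminated patients is wrong at any PF threshold. The plan names intubation rate and 28-day mortality as outcomes, and then removes patients escalated to intubation under these criteria.

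**What to change.** 1. **Analysis set.** Replace the exclusion sentence. Analyse intubation and 28-day mortality in all randomised patients. Keep terminated patients in the primary mixed model: those without a 1-hour rate contribute their baseline rate, and those terminated on the 1-hour gas also contribute the rate observed at that time. Add a sensitivity analysis that gives patients intubated before 1 hour the worst rank. Define the modified intention-to-treat set accordingly.
2. **PF criterion.** Express it as a deterioration from the patient's baseline, as the MAP criterion already is relative to baseline, with the size set by the clinical team. State the time on treatment from which it applies, and whether it applies to the 1-hour gas. A baseline PF is already needed for the PF outcome and the HACOR score, but the plan should state what FiO2 is assigned to the reservoir mask.
3. **Recording.** Record the triggering criterion and its time, and report counts by criterion and arm.

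The cost is protocol and SAP wording, one case-report field, and 28-day status for terminated patients. No extra patients or scheduled blood gases are needed. If enrolment is already over, the change to the analysis set can still be made for every terminated patient whose outcome data can be recovered.

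### Patients intubated under the early termination criteria are dropped from every analysis, so as written their intubations and deaths are missing from two stated outcomes

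*Combined protocol and SAP*

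**What the plan says.** The Objective includes "intubation rate, and 28-days mortality" among the terms of comparison, and Study End Points lists "6) intubation rate and (7) mortality rate 28-days" as secondary outcomes.

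The Protocol section sets early termination criteria, among them "worsening of respiratory failure (respiratory > 35 breaths/min". It continues: "If one or more of the criteria were encountered, intervention was escalated to intubation and mechanical ventilation". The next sentence is "These patients were excluded from the final data analyses". On who decides: "The decision was made by the managing physician without the involvement of the researcher team". For the period after the 60-minute protocol it says that "the chosen modality was continued at the discretion of the treating physician".

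Physiological measurements "were obtained before beginning of the ventilation procedure and at 1 hour of ventilation", and at no other time. The Statistical Analysis Plan claims a modified intention-to-treat analysis fixed in advance. It does not say what the modification is, and it returns the excluded patients to no analysis.

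**The concern.** For a patient who meets a criterion, being intubated is both the event that outcome 6 should count and the reason for leaving the data set. A later death in that patient is lost from outcome 7. The patients removed are those in whom the assigned device failed, so the two outcomes that should show a difference in failure are the ones that cannot. If failure is equal in both arms, the reported rates are still too low.

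The exclusion also follows randomisation and depends on response. A respiratory rate above 35 is a trigger, and respiratory rate is the primary variable. Removing such patients can distort the primary comparison if failure is more common in one arm, or if failure is more closely tied to respiratory rate in one arm.

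**Working it through.** **Reading the text.** The core conclusion needs no arithmetic. Patients escalated under the criteria leave the final analyses, no outcome is exempted, and intubation and 28-day death are outcomes. Intubations and deaths in patients who never met a criterion are still counted.

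**Inputs for size.** From Sample Size: 94 per group, 10% attrition, respiratory rate 31 (SD 3.7) to 22 (SD 4.1) on HFNC and 31 (SD 3.9) to 25 (SD 3.6) in control. The 94 is taken as planned; how it was derived does not affect this point. Failure rates, later intubations, death risks and correlations are not in the documents and are assumed. Early failures out of 94 are 5 at 5%, 9 at 10% and 19 at 20%.

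**Intubation** (4 later intubations per arm; Fisher exact test):

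| Early failure | All randomised | p | After exclusion | p |
|---|---|---|---|---|
| 10% v 10% | 13/94 v 13/94 | – | 4/85 v 4/85 | – |
| 5% v 10% | 9/94 v 13/94 | 0.50 | 4/89 v 4/85 | 1.0 |
| 5% v 20% | 9/94 v 23/94 | 0.011 | 4/89 v 4/75 | 1.0 |

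In the first row 9/13 = 69% of intubations are lost. In the second, no significant result is lost. The third does not hinge on the 4 later events: with 0, 2 or 8 per arm, p in all randomised patients is 0.004, 0.007 or 0.020. After exclusion there are no events, p = 1.0, or p = 0.80.

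**Deaths.** Let p be the early failure rate, d the risk of death after early intubation, and 5% the risk in other patients. The share of deaths lost is p·d / [p·d + (1 − p)·0.05]. At p = 10% and d = 0.2 this is 0.020/(0.020 + 0.045) = 31%. For d from 0.2 to 0.4 the share is 17–30% at p = 5%, 31–47% at 10% and 50–67% at 20%.

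**Primary outcome.** The pooled 1-hour SD is √[(4.1² + 3.6²)/2] = 3.86. Suppose the share p with the highest failure propensity is removed, and propensity has correlation ρ with respiratory rate. The mean of those left falls by ρ × SD × k(p), where k(p) = φ(z)/(1 − p) and z is the upper-p normal quantile. This gives k = 0.1086, 0.1950 and 0.3500 at 5%, 10% and 20%.

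- Same ρ in both arms (0.3 to 0.5), 5% v 10%: ρ × 3.86 × (0.1950 − 0.1086) = 0.10 to 0.17 breaths/min.
- Same ρ, 5% v 20%: ρ × 3.86 × (0.3500 − 0.1086) = 0.28 to 0.47.
- Equal 10% failure, ρ = 0.5 in one arm and 0 in the other: 0.5 × 3.86 × 0.1950 = 0.38. With 0.3 and 0 it is 0.23.

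With the same ρ the shift favours the arm that fails more often. On the change score, the baseline SD is √[(3.7² + 3.9²)/2] = 3.80, and the change SD is 5.42, 3.83 or 2.42 for an assumed baseline-to-1-hour correlation of 0, 0.5 or 0.8. The 0.38 then becomes 0.53, 0.37 or 0.24.

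**The case against.** The best defence is that the authors cannot have meant it. Listing intubation as an outcome and then removing intubated patients is close to a contradiction, and the exclusion sentence sits between the 60-minute protocol and the baseline and 1-hour measurements. It may have been meant only for the physiological comparisons, since these patients have no 1-hour value on the assigned device. Or it may apply only within the first 60 minutes, so that later intubations count. Both readings are possible, but the text confirms neither. Under the second, early failures are still lost from both outcomes.

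That the managing physician decides without the researchers limits their influence. It does not stop the exclusion from depending on response. The attrition allowance covers lost numbers, not selection.

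Some of the objection stands. Every scenario is illustrative, and only the 5% v 20% set changes a conclusion. The plan's default test is chi-square, which gives 0.36 and 0.0066 in place of 0.50 and 0.011; no conclusion changes. The shifts in the primary outcome are small against the planned difference of 3 breaths/min. With equal failure and the same link to respiratory rate in both arms, bias is close to nil; the 0.38 needs a contrast between arms that nothing in the documents supports. That part is secondary.

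**Conclusion.** The concern holds. On the text as written, criteria-driven intubations, and deaths among those patients, are omitted from two outcomes the trial sets out to compare. That rests on the wording alone and takes effect as soon as one patient terminates early. How many events are lost depends on failure rates the documents do not give; under the assumptions above it ranges from 17% to 67% of deaths, and is 69% of intubations in the 10% case. Bias in the primary comparison is possible, but its direction and size cannot be determined from the documents. The intubation and mortality problem is enough on its own to require correction.

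**What to change.** Delete the exclusion sentence. State that intubation and 28-day mortality are analysed in all randomised patients by assigned arm, with early-terminated patients followed to day 28. Define the modified intention-to-treat set, and state the time window to which early termination refers. Leave the termination criteria as they are.

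For the primary outcome, pre-specify how early-terminated patients are kept, at least in a sensitivity analysis, and label any completers analysis as such. The options are:

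- Worst rank on the change in respiratory rate. This is a composite of respiratory rate and device failure, so it changes the estimand and must be labelled.
- The last value before escalation, where one was recorded; the plan schedules none between baseline and 1 hour.
- The mixed model already named in the plan, which can retain patients with only a baseline value under missingness at random. That assumption is doubtful when a high respiratory rate is itself a trigger, so it needs sensitivity analyses.

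The cost is text changes, 28-day vital status for patients who would have been dropped, and one added analysis. Worst rank can also cost power. The table gives simulated power (changes of −9 v −6, 94 per arm, failure correlation 0.3) for change SD 5.42 / 3.83 / 2.42. Both significance levels are shown because Sample Size uses 1% and the Statistical Analysis Plan 0.05.

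| Early failure | Power at 1% | Power at 5% |
|---|---|---|
| 10% in both arms | 64 / 94 / 100% | 83 / 99 / 100% |
| 20% in the arm with the lower rate, 5% in the other | 12 / 41 / 94% | 27 / 66 / 99% |

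If failure is the other way round (5% in the arm with the lower rate, 20% in the other), power at 1% is about 96%, 100% and 100%. The loss arises where the effect on respiratory rate and the effect on failure point in opposite directions.

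### With only two measurement times, the planned repeated-measures ANOVA is an unadjusted change-score test; adjusting for baseline respiratory rate would be modestly more precise

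*Combined protocol and SAP*

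**What the plan says.** Under Study End Points, "The primary outcome was a reduction in respiratory rate from prior to randomization to at 1 hour of treatment". The preceding paragraph on measurements says that respiratory rate and the other physiological variables "were obtained before beginning of the ventilation procedure and at 1 hour of ventilation", so each patient has two values at most.

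The Statistical Analysis Plan states that "Primary outcome of respiratory rate difference and other normally distributed secondary outcomes were calculated using repeated measure ANOVA", and describes this as "a generalized mixed model with a compound-symmetry covariance matrix". No baseline covariate, analysis of covariance or constrained-baseline model appears anywhere. The plan does not say which model term is the primary test. It gives neither the correlation between baseline and 1-hour rates nor the SD of the change.

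**The concern.** A repeated-measures model with two times can look as if it already makes good use of the baseline value. It does not adjust for it. If the test is group-by-time, the analysis subtracts each patient's full baseline from the 1-hour value, which assumes that a patient who starts one breath higher also ends one breath higher.

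Entry requires "respiratory rate $>$ 30 breath per minute", so patients are selected for high values and some regression toward the mean is expected. A slope below 1 is therefore plausible. In that case the change score carries noise that a fitted slope would remove, and it over-corrects any chance difference between arms at baseline. The Methods describe permuted blocks with no stratification on respiratory rate, so such a difference is left to chance. At stake is the width of the interval for the primary effect and its sensitivity to baseline imbalance. The validity of the test is not in question.

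**Working it through.** **The plan's own figure.** Sample Size gives 94 per group (90% power, two-sided 1% error, 10% attrition). The inputs are 31 (SD 3.7) to 22 (SD 4.1) with HFNC and 31 (SD 3.9) to 25 (SD 3.6) in control, a difference of 9 − 6 = 3 breaths/min. A two-sample t-test on 1-hour values (pooled SD 3.86) needs 51 per arm, or 57 after attrition, so 94 is not reproduced that way. An SD of change near 5.0 (correlation about 0.15) gives 85 per arm, and 94 when 10% is added. The discrepancy is a separate matter. Here it only suggests a low correlation as one plausible case.

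**Step 1: the identity.** With two complete times, the group-by-time contrast is the between-arm difference in mean change, and its error variance is the pooled variance of the change. The compound-symmetry assumption does not alter this. On simulated data with 85 per arm, the change-score t and the group-by-time statistic from a random-intercept mixed model were both −5.4483.

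**Step 2: inputs.**
- Pooled 1-hour SD: s1 = √((4.1² + 3.6²)/2) = 3.858.
- Pooled baseline SD as stated: √((3.7² + 3.9²)/2) = 3.80.
- Baseline SD after the entry threshold, treating baseline as normal with mean 31 and SD 3.80: for a cut at 30, a = (30 − 31)/3.80 = −0.263, λ = φ(a)/(1 − Φ(a)) = 0.638, and SD = 3.80 × √(1 + aλ − λ²) = 2.48. A cut at 30.5 gives 2.38. I use s0 = 2.4.
- Completers: 94 × 0.9 = 84.6, taken as 85 per arm.
- Correlation ρ: not documented, so a range is assumed.

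**Step 3: variances.** Change-score variance = s0² + s1² − 2ρ·s0·s1. Baseline-adjusted residual variance = s1²(1 − ρ²). SE = √(2 × variance/85).

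At ρ = 0.3: change 5.76 + 14.885 − 5.556 = 15.09; adjusted 14.885 × 0.91 = 13.55; ratio 0.898.

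| ρ (enrolled sample) | 0.15 | 0.3 | 0.5 |
|---|---|---|---|
| Variance ratio, adjusted/change | 0.814 | 0.898 | 0.981 |
| SE, change | 0.648 | 0.596 | 0.518 |
| SE, adjusted | 0.585 | 0.565 | 0.513 |
| 95% half-width, change | 1.28 | 1.18 | 1.02 |
| 95% half-width, adjusted | 1.16 | 1.12 | 1.01 |
| Change-score n per arm to match (85/ratio) | 104 | 95 | 87 |
| Power at 3 breaths, α 0.05, change | 0.9959 | 0.9988 | 0.9999 |
| Power at 3 breaths, α 0.05, adjusted | 0.9991 | 0.9996 | 0.9999 |
| Power at 3 breaths, α 0.01, change | 0.9775 | 0.9920 | 0.9992 |
| Power at 3 breaths, α 0.01, adjusted | 0.9938 | 0.9964 | 0.9994 |

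Power is from the noncentral t. Both error levels are shown because Sample Size uses 1% and the analysis section 5%. The gain is zero where the slope ρ·s1/s0 equals 1, that is at ρ = 2.4/3.858 = 0.62.

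**Step 4: other readings of ρ.**
- If ρ is the correlation before the entry cut, the slope is b = ρ × 3.858/3.80 and the change variance is (b − 1)² × 2.477² + s1²(1 − ρ²). The ratio is 0.77, 0.82, 0.88 and 0.94 for ρ = 0.15, 0.3, 0.5 and 0.7 (SE 12%, 9%, 6% and 3% smaller).
- With the stated SDs and no truncation, the ratio runs from 0.58 to 0.86 over ρ = 0.15 to 0.7. This is the most favourable case for adjustment over that range.

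**Step 5: chance imbalance.** The 95% limit for the baseline difference between arms is 1.96 × 2.4 × √(2/85) = 0.72 breaths/min. The change score moves by (1 − slope) × 0.72. Slopes of 0.24, 0.48 and 0.80 give shifts of 0.55, 0.37 and 0.14 breaths/min.

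**The case against.** The strongest reply is that nothing is broken. The endpoint is a reduction, a change-based test targets exactly that, and under randomization it is unbiased. In the main scenario the half-width shrinks by only 0.12, 0.06 or 0.01 breaths/min, for a rate counted in whole breaths and a planned difference of 3. All of that stands, and it is why this is only a suggestion.

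The size is also soft. At ρ = 0.5 the SE gain is 1%, 6% or 13% depending on how the entry threshold is handled. The baseline SD of 2.4 is constructed: the cut implies an enrolled mean near 33.4 rather than 31, and the main scenario leaves the 1-hour SD untruncated. The figures are therefore a range and not an estimate. The direction does not depend on them: apart from the one degree of freedom, the adjusted variance is never larger.

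The equivalence holds only if group-by-time is the test and pairs are complete. The plan does not name the term. The group main effect would average in the baseline and halve the expected difference to (0 + 3)/2 = 1.5. This is a further reason to specify the analysis. Patients with a baseline value only would drop out of the proposed regression, but they carry almost no information on the effect.

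Finally, the document is dated 31 May 2018, within a January to December 2018 study, and is written in the past tense. A change of primary analysis would need a dated amendment. That affects the cost and how the change is labelled, not the statistical point.

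**Conclusion.** The point holds as an optional improvement. The planned test, read as group-by-time on complete pairs, is a valid change-score t-test with no baseline adjustment. Adjusting would make the standard error about 1% to 10% smaller for enrolled-sample correlations of 0.5 down to 0.15 with a baseline SD of 2.4. If the stated SDs applied without truncation, the reduction at the same correlations would be about 13% to 24% (1 − √0.76 and 1 − √0.58). There is no gain when the slope is 1.

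Power at 3 breaths/min is already at least 99.6% at α 0.05 and 97.8% at α 0.01 in the main scenario, so the benefit lies in the interval and in protection against baseline imbalance. The algebra is certain; the magnitudes rest on an undocumented correlation and an assumed normal baseline cut at the entry threshold. Adjustment does nothing about early-terminated patients, of whom the Protocol section says "These patients were excluded from the final data analyses". That is a separate issue.

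**What to change.** Replace the sentence on the primary analysis with wording such as:

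> The primary analysis is a linear model of 1-hour respiratory rate on treatment arm with baseline respiratory rate as covariate, reporting the adjusted mean difference and 95% confidence interval. Secondary outcomes treated as normally distributed use the same model with their own baseline. Repeated-measures ANOVA, tested on the group-by-time term, is a sensitivity analysis.

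Ordinal or skewed outcomes keep the method already planned. The change uses the same data and software and costs at most one degree of freedom per model. It should be made by dated amendment before results are seen. If results have already been seen, keep the planned model as primary, state that group-by-time is the test, and report the adjusted model as a sensitivity analysis.
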